4. Determine the efficacy of three doses of VGX-3100 as measured by virologic clearance of HPV-16 and/or HPV-18 by intra-anal swab testing	4. Proportion of subjects with no evidence of HPV-16 and/or HPV-18 from intra-anal swab by specific HPV testing at Week 36
5. Determine the efficacy of three doses of VGX-3100 as measured by complete histopathologic regression of anal or anal/peri-anal HSIL to normal tissue	5. Proportion of subjects with no evidence ¹⁰ of anal or anal/peri-anal Low grade squamous intraepithelial lesion (LSIL) or HSIL (i.e. no evidence of AIN2, AIN3, PAIN2, PAIN3) on histology (i.e. biopsies or excisional treatment) at Week 36
6. Determine the efficacy of three doses of VGX-3100 as measured by histopathologic non-progression of anal or anal/peri-anal HSIL	6. Proportion of subjects with no progression ¹¹ of anal or anal/peri-anal HSIL to carcinoma from baseline to histology (i.e. biopsies or excisional treatment) at Week 36
7. Describe the efficacy of VGX-3100 for partial responders , as measured by reduction in the number of intra-anal and/or peri-anal qualifying lesion(s), as applicable and the reduction in size of peri-anal lesion(s) if present, and for whom the disease has not progressed according to Investigator judgment in subjects who did not have anal or anal/peri-anal HSIL lesion resolution at Week 36	7. Percent reduction in the number of qualifying ¹² intra-anal and/or peri-anal lesion(s), and the reduction in size of peri-anal lesion(s) as determined by the Investigator at Weeks 36, 64, and 88 compared to baseline ¹³ .
8. Determine the cellular immune response following dose 3 and compared to baseline	8. Flow Cytometry response magnitude at baseline and Week 15

9. Determine the efficacy of three doses of VGX-3100 with respect to histopathologic regression of anal or anal/peri-anal HSIL or virologic clearance of HPV-16 and/or HPV-18
	
9. Proportion of subjects with no histologic evidence of anal or anal/peri-anal HSIL by histology (i.e., collected via biopsy or excisional treatment) or no evidence of HPV-16/18 at Week 36 from intra-anal and/or peri-anal lesion tissue

---	---

⁹ Clearance of HPV-16 or HPV-18 is defined as being undetectable by PCR assay.

¹⁰ No evidence of anal or anal/peri-anal HSIL is defined as normal tissue or anal or anal/peri-anal LSIL.

¹¹ Progression is defined as advancement to carcinoma by histology according to the Pathology Adjudication Committee.

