¹² An intra-anal and/or peri-anal lesion which is confirmed to be HPV-16 and/or HPV-18 positive and have histologically confirmed anal or anal/peri-anal HSIL evaluated by the Pathology Adjudication Committee (PAC).

¹³ Baseline photographic imaging is defined as photographs obtained pre-biopsy at Screening, or post biopsy at Screening (for subjects with historical biopsy tissue).

Exploratory Objectives	Associated Exploratory Endpoints
1. Describe the long term efficacy of VGX-3100 with respect to combined histopathologic regression of anal or anal/peri-anal HSIL and virologic clearance of HPV-16 and/or HPV-18	1. Proportion of subjects with no histologic evidence of anal or anal/peri-anal HSIL on histology (i.e. collected via biopsy or excisional treatment) and no evidence of HPV-16/18 at Week 64 by testing from intra-anal and/or peri-anal lesion tissue
2. Describe the long term efficacy of VGX-3100, as measured by histologic regression of anal or anal/peri-anal HSIL	2. Proportion of subjects with no evidence of anal or anal/peri-anal HSIL on histology (i.e. biopsies or excisional treatment) at Week 64
3. Describe the long term efficacy of VGX-3100, as measured by virologic clearance of HPV-16 and/or HPV-18 by testing from lesion tissue	3. Proportion of subjects with no HPV-16/18 at Week 64 by testing from intra-anal and/or peri-anal lesion tissue
4. Describe the long term efficacy of VGX-3100, as measured by virologic clearance of HPV-16 and/or HPV-18 by intra-anal swab testing	4. Proportion of subjects with no evidence of HPV-16 and/or HPV-18 from intra-anal swab by specific HPV testing at Week 64 and Week 88
5. Evaluate tissue immune responses to VGX-3100 in intra-anal and/or peri-anal samples	5. Assessment of proinflammatory and immunosuppressive elements in tissue, where feasible ¹⁴
6. Describe the clearance of HPV-16 and/or HPV-18 infection from non-anal anatomic locations	6. Proportion of subjects who have cleared HPV-16 and/or HPV-18 on specimens from non-anal anatomic locations as applicable based upon gender (i.e. oropharynx, cervical, vaginal, and penile at Week 36)
7. Describe the association of microRNA (miRNA) profile, previous anoscopy, cytology and HPV testing results with Week 36 histologic regression	7. HRA, cytology, and HPV test results and miRNA profile (baseline and at the Weeks 15 and 36) in conjunction with histologic regression of anal or anal/peri-anal HSIL at Week 36

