Data Safety & Monitoring Board (DSMB): An independent DSMB will meet quarterly to review safety data and tissue regression and viral clearance results. The DSMB will be charged with advising the Sponsor if there appears to be a safety issue. No formal interim analysis is planned. Refer to Section 3.8 for stopping rule criteria.

Definition of Responder and Non-Responder:

Responder and non-responder definitions (**Table 2 through Table 7**) take into account both histopathologic regression of anal or anal/peri-anal HSIL **and** virologic (HPV-16/18) clearance as measured by intra-anal and/or peri-anal tissue, since HPV persistence is an important factor in the clinical progression of HSIL. Any case of histologically confirmed progression from HPV-16/18 positive anal or anal/peri-anal HSIL to carcinoma according to the PAC is considered a non-responder.

Table 2: Definition of Responder and Non-Responder for Composite Endpoint of Regression and Clearance	
Responder	Non-Responder
No histologic evidence of anal or anal/peri-anal HSIL AND Negative PCR for HPV-16 or HPV-18 in anal lesion tissue AND No non-study treatment of curative intent of intra-anal and/or peri-anal lesions	Histologic evidence of anal or anal/peri-anal HSIL, anal Adenocarcinoma-in-situ (AIS), anal or anal/peri-anal carcinoma OR PCR positive for HPV-16 or HPV-18 in anal lesion tissue OR Any non-study treatment of curative intent of intra-anal and/or peri-anal lesions

Table 3: Definition of Responder and Non-responder for HSIL Regression Endpoint

Responder	Non-Responder
No histologic evidence of anal or anal/peri-anal HSIL 
AND
 No non-study treatment of curative intent of intra-anal and/or peri-anal HSIL	Histologic evidence of anal or anal/peri-anal HSIL or carcinoma at evaluation 
OR
 Any non-study treatment of curative intent of intra-anal and/or peri-anal HSIL

Table 4: Definition of Responder and Non-responder for Viral Clearance Endpoint

Responder	Non-Responder
No evidence of HPV-16 or HPV-18 in tissue/swab at evaluation 
AND
 No non-study treatment of curative intent of intra-anal and/or peri-anal HSIL	Evidence of HPV-16 or HPV-18 in tissue/swab at evaluation 
OR
 Any non-study treatment of curative intent of intra-anal and/or peri-anal HSIL

Table 5: Definition of Responder and Non-responder for Complete HSIL Regression Endpoint

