4.0 TRIAL POPULATION

4.1 INCLUSION CRITERIA

1. Must understand, agree and be able to comply with the requirements of the protocol and be able to provide voluntary consent to participate and sign an Informed Consent Form (ICF) prior to study-related activities;
2. Age 18 years and above;
3. Negative screening test for HIV-1/2^a within 30 days of Dose 1;
4. Confirmed anal or anal/peri-anal HPV-16/18 infection at Screening by PCR from HSIL specimen;
5. Anal tissue (blocks only) provided to the Study PAC for diagnosis must be collected within 10 weeks of first dose of VGX-3100;
6. At least one anal or anal/peri-anal (AIN2/3 and/or PAIN2/PAIN3) lesion that is histologically-confirmed as HSIL by the PAC at Screening;
 - i. The lesion needs to be large enough to biopsy, but the biopsy ($\geq 4\text{mm}$) should not remove the entire lesion in order to allow for continued lesion measurement while on the study;
7. Investigator judges the subject to be an appropriate candidate for histology collection procedures (i.e. excision or biopsy);
8. Female subjects, must meet one of the following criteria with respect to their reproductive capacity:
 - i. Post-menopausal as defined by spontaneous amenorrhea for more than 12 months or spontaneous amenorrhea for 6-12 months with follicle-stimulating hormone (FSH) level $>40\text{mIU/mL}$;
 - ii. Surgically sterile due to absence of ovaries or due to a bilateral tubal ligation/occlusion performed more than 3 months prior to Screening;
 - iii. Subject agreement to avoid pregnancy one month after last dose of IP (Week 12 or Week 40);
 - iv. Women of Childbearing Potential (WOCBP) are willing to use a contraceptive method with failure rate of less than 1% per year when used consistently and correctly from Screening until one month following the last dose of IP (Week 12 or Week 40). The following are acceptable methods:
 1. Hormonal contraception: either combined or progestin-alone including oral contraceptives, injectable, implants, vaginal ring, or percutaneous patches. Hormonal contraceptives must not be used in subjects with a history of hypercoagulability (e.g. deep vein thrombosis, pulmonary embolism);
 2. Abstinence from penile-vaginal intercourse when this is the subject's preferred and usual lifestyle;
 3. Intrauterine device or intrauterine system;

4. Male partner sterilization at least 6 months prior to the female subject's entry into the study, and this male is the sole partner for that subject;

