8.5.2 SECONDARY ANALYSES

The secondary efficacy binary endpoints will be analyzed in the same manner as the primary hypothesis, but without the hypothesis test p-values. The efficacy time frame is defined in the same manner as for the primary endpoint. All of the efficacy binary endpoints will be analyzed in two ways: a) based on all lesions and b) based on qualifying and new lesions.

The anatomic extent endpoint will be analyzed by calculating the mean percent change in surface area and the mean percent change in number of lesions and associated 95% t-distribution based confidence intervals.

Post-baseline increases in Flow responses will be summarized with medians and 95% CIs. Valid samples for statistical analysis purposes will be those collected within 14 days of the specified visits. Baseline is defined as the last measurement prior to the first treatment administration.

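### The intra-anal swab clearance endpoints count subjects who were swab-negative before dosing as viral-clearance responders

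*Protocol*

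**What the plan says.** All references are to the Version 3.0 text.

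- **Responder rule.** Synopsis Table 4 requires "No evidence of HPV-16 or HPV-18 in tissue/swab at evaluation" together with no curative treatment outside the study. It has no baseline condition. Table 6 (non-progression), by contrast, does refer to baseline.
- **Definition of clearance.** Synopsis footnote 9 reads "Clearance of HPV-16 or HPV-18 is defined as being undetectable by PCR assay". It is attached to secondary endpoint 3, the tissue endpoint.
- **Swab endpoints.** Secondary endpoint 4 is "Proportion of subjects with no evidence of HPV-16 and/or HPV-18 from intra-anal swab by specific HPV testing at Week 36". Its objective is efficacy "as measured by virologic clearance of HPV-16 and/or HPV-18 by intra-anal swab testing". Exploratory endpoint 4 repeats the measure "from intra-anal swab by specific HPV testing at Week 64 and Week 88".
- **Non-anal endpoint.** Exploratory endpoint 6 is "Proportion of subjects who have cleared HPV-16 and/or HPV-18 on specimens from non-anal anatomic locations", and gender is the only restriction stated.
- **Eligibility.** Section 4.1, criterion 4: "Confirmed anal or anal/peri-anal HPV-16/18 infection at Screening by PCR from HSIL specimen". No criterion concerns a swab or rinse result.
- **Analysis.** Section 8.5.2: "The secondary efficacy binary endpoints will be analyzed in the same manner as the primary hypothesis, but without the hypothesis test p-values". Section 8.5.9 says the same for the exploratory endpoints. Section 8.4 makes mITT, meaning everyone who received at least one dose, primary for efficacy.
- **Sampling.** Table 8 schedules anal swabs at Screening and Day 0, and oropharyngeal and genital samples from Day 0.

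**The concern.** The swab objective speaks of efficacy through clearance of virus, but the rule counts absence of virus at one visit. The two agree only if every subject carried HPV-16/18 on the intra-anal swab before dosing. Eligibility ensures this for the lesion specimen and not for the swab. A subject negative before and after treatment had nothing to clear at that site, yet adds one to both numerator and denominator.

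In a single-arm trial no control group would carry the same share of baseline negatives and so reveal the effect. Section 1.1 also cites one-year high-risk HPV clearance of 56% to 78% and treats such data as part of the historical control. Those figures concern clearance of existing anal infection. A proportion that includes never-positive subjects is not comparable with them.

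**Working it through.** **Plan's own figure.** The protocol states no expected rate for the swab endpoints. Its only related figure is about 80% power for the primary endpoint (Section 8.6: 24 subjects, 40% versus 15%, 90% evaluable; Section 8.5.1: one-sided exact test at 0.05). With 24 × 0.9 = 21.6, rounded down to 21 evaluable, the test rejects at 7 or more responders, with attained alpha 0.029 and power 0.800. With all 24 it rejects at 8 or more, with alpha 0.020 and power 0.808. The figure reproduces, and the present point does not touch it.

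**Formula.** Let s be the proportion swab-positive for HPV-16/18 before dosing, c the proportion of those undetectable at evaluation, and i the proportion of baseline negatives newly positive at evaluation. Assume every subject has an evaluation swab and none had curative treatment outside the study.

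- Reported under Table 4: (1−s)(1−i) + s·c
- Intended quantity: c
- Excess: (1−s)(1−i) + s·c − c = (1−s)(1−i−c)

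The excess is positive whenever s < 1 and i + c < 1. It is zero at s = 1.

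**Numbers.** The protocol gives none of s, c or i, so every entry is an assumption.

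| s | c = 20%, i = 0 | c = 20%, i = 10% | c = 40%, i = 0 | c = 40%, i = 10% |
|---|---|---|---|---|
| 100% | 20% | 20% | 40% | 40% |
| 90% | 28% | 27% | 46% | 45% |
| 80% | 36% | 34% | 52% | 50% |
| 60% | 52% | 48% | 64% | 60% |

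For example, s = 80%, c = 20%, i = 0 gives 0.20 + 0.80 × 0.20 = 0.36, an excess of 0.20 × 0.80 = 0.16. At s = 60% it is 0.40 + 0.60 × 0.20 = 0.52, an excess of 0.32.

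**In counts.** Suppose 18 of 24 subjects are swab-positive at baseline and 6 of them clear, while the other 6 are negative throughout. Table 4 gives 12/24 = 50% (95% Clopper-Pearson interval 29% to 71%). Among baseline positives the result is 6/18 = 33% (13% to 59%).

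**The case against.** The strongest reply is that little depends on these endpoints. They carry no hypothesis test, and the protocol calls the swabs a less invasive, exploratory measure. The fourth-dose option rests on histology and lesion extent. Secondary endpoint 4, read literally, is a proportion with no evidence of virus, which is what gets counted, and the baseline samples would allow another tabulation later. This limits the consequence but does not remove the error, because the objective and the title of Table 4 present the count as clearance. Nor is the matter left to another document: Section 8.1 says the formal analysis plan is Section 8 itself, and Table 4 fixes the rule.

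The size is also open to challenge. If all subjects are swab-positive at baseline there is no inflation. New detection among baseline negatives reduces it, and so does the treatment condition in Table 4 when it makes a baseline negative a non-responder. All of this stands, so only a conditional size can be given.

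A reader might infer that never-positive subjects are also counted as cleared at oropharyngeal and genital sites, where assumed positivity of 5% to 20% with no clearance and no new detection would give 95% to 80% cleared. The documents do not establish this. Exploratory endpoint 6 speaks of having cleared, which may presuppose a prior positive. Table 4 names tissue and swab, whereas the oropharyngeal sample is a rinse, and footnote 9 belongs to the tissue endpoint. What can be said is that the denominator is not stated beyond gender.

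**Conclusion.** The point holds for secondary endpoint 4 and exploratory endpoint 4. Applied as written, Table 4 credits baseline swab-negative subjects as viral-clearance responders, and the reported proportion exceeds true clearance by (1−s)(1−i−c). Under the assumptions c = 20% and i = 0, that is 16 points at s = 80% and 32 points at s = 60%. It is zero at s = 100%. The actual size cannot be derived from the protocol.

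A reader might infer that viral clearance is overstated throughout the trial. It is not: the primary composite and secondary endpoint 3 rest on lesion tissue, which must be HPV-16/18 positive at entry. Nor does the argument need subjects with peri-anal disease only. The wording of criterion 6 can be read to admit them, but a negative baseline swab in any subject is enough. For exploratory endpoint 6 the finding is an unstated denominator, which should be fixed in the same way.

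**What to change.** In Table 4 (swab part) and in exploratory endpoint 6:

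- **Denominator.** Use mITT subjects positive for HPV-16 and/or HPV-18 at that site before the first dose. For the swab endpoints, a positive intra-anal swab at either Screening or Day 0 qualifies. For non-anal sites, use the Day 0 sample. State this explicitly, because Section 8.5.2 defines baseline as the last pre-treatment measurement, which would drop a subject positive at Screening but negative at Day 0.
- **Assay.** Use the same type-specific PCR assay at baseline and evaluation, SPF10 for anal swabs. Section 6.17 schedules the Cobas test only at Screening and Weeks 36 and 64, so it cannot pair with Day 0 or Week 88.
- **Responder.** Neither type detected at evaluation and no curative treatment outside the study, with a Clopper-Pearson interval on that denominator.
- **Separate reporting.** Give undetectability at the visit among all subjects, and new positivity among baseline negatives, under those names.

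Leave footnote 9 and the tissue endpoint as they are. The samples are already scheduled, so the change is one of wording and tabulation. Its cost is smaller denominators and wider intervals on endpoints that carry no test.

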1.0 INTRODUCTION

1.1 BACKGROUND AND SCIENTIFIC RATIONALE

Infection with human papillomavirus (HPV) can lead to malignant neoplasia, localized primarily in the ano-genital area and aero-digestive tract, in both men and women. Human Papillomavirus types tropic to mucosal tissues are classified into high-risk (HR), based on their potential to cause cancer, and low-risk (LR) (causing generally benign lesions). In the United States (US), approximately 14 million new genital HPV infections occur annually, and approximately half of these infections are with a high-risk HPV type (HR-HPV) and thus can cause cancer [2]. In U.S. adults through age 59 years, about 25% of men and 20% of women have genital HR-HPV infection [3]. Human Papillomavirus causes more cancers than any other virus. In U.S. archival tissues of cancers diagnosed from 1993 to 2005, HPV Deoxyribonucleic Acid (DNA) was detected in 68.8% of vulvar, 90.6% of cervical, 91.1% of anal, 75.0% of vaginal, 70.1% of oropharyngeal (OP), 63.3% of penile, 32.0% of oral cavity, and 20.9% of laryngeal cancers, as well as in 98.8% of cervical cancer in situ (CCIS) [4]. An average of over 30,000 cases per year of HPV-attributable cancer were diagnosed during the period 2008 through 2012 in the U.S. [5]. Human Papillomavirus-16 and HPV-18 are the most significant among high-risk types since they are responsible for most HPV-caused cancers [4].

With regard to anal cancer, about 95% of cases are caused by HPV, and most of those cases are caused by HPV-16 [6, 7]; with some by HPV-18 and perhaps other HPV genotypes [2]. An estimated 8,300 new cases of anal cancer in the US are diagnosed each year (for year 2017), with an estimated 1,280 deaths annually due to this cancer [8]. In Canada, the latest available data is for year 2013, during which 580 new cases of anal cancer were diagnosed and 144 persons died due to anal cancer [9].

The precursor lesion to HPV-associated anal cancer historically was known as anal high-grade dysplasia or intraepithelial neoplasia. In 2012, the Lower Anogenital Squamous Terminology (LAST) Standardization Project for HPV-associated lesions applied the term HSIL to encompass high grade dysplasia [10]. Among HPV-associated anal HSIL cases in the US, about 55% to 80% are associated with HPV-16/18, and worldwide about 80% of cases are associated with HPV-16/18 [7, 11, 12].

Left untreated, anal HSIL may progress to cancer. Spontaneous regression of these lesions may occur, but the available data indicate that such regression is in the minority of cases. For example, published results of a small observational study of anal HSIL in men who have sex with men (MSM) in Australia found spontaneous regression occurred in 29% of those HIV-negative after more than one year of follow-up time, with an even lower regression rate in those who were HIV-positive. That study also found that the majority (71%) of patients who regressed only did so to anal low-grade SIL (Low grade squamous intraepithelial lesion [LSIL]), with the remainder to normal tissue [13]. In an ongoing larger observational study of gay and bisexual men – the Study of the Prevention of Anal Cancer (SPANAC) [14] -- also comprised of patients HIV-negative and HIV-positive (though with medically well-controlled CD4 cell counts), preliminary published data show that 55% of patients with anal HSIL, regardless of HIV status, had their HSIL persist to at least 12 months and HPV-16 was significantly associated with persistence as compared to other HPV genotypes (Relative Risk of 1.5) [15].

Spontaneous regression data from that study are not yet published, but preliminary data show spontaneous regression of only about 20% by one year of follow-up. Further, many of those patients who regressed later recurred to HSIL, suggesting that HSIL in some cases may be merely regressing to a level below the detection limit but is still present [16]. Other published data from a sub-study of that larger study indicate that HPV-16 E6-specific T-cell responses may be associated with recent anal HSIL regression (Pexact = 0.065) [17]. That finding provides further plausibility, in addition to other data summarized later in this protocol, that VGX-3100 plus electroporation treatment could cause anal HSIL regression.

Anal HPV infection spontaneous clearance in non-immunocompromised adults can occur, but such data are generally unavailable for persons who have anal HSIL. Nevertheless, high-risk HPV (HR-HPV) clearance by one year ranges from 56% to 78%, varying by gender and sexual preference etc., as found in large, prospective studies [18-20] with some wider variation in clearance rates for HPV-16 and HPV-18 specifically in those studies.

Collectively, the aforementioned anal HSIL regression and HPV clearance data comprise in part the historical control data that the results of the present trial will be compared to.

1.1.1 VGX-3100

VGX-3100 contains plasmids that target HPV-16 E6/E7 and HPV-18 E6/E7 antigens. The plasmids were designed and constructed using proprietary synthetic vaccine (SynCon™) technology. This process involves synthetically deriving consensus genes across multiple strains and optimizing DNA inserts at the genetic level to allow high expression in human cells. Together, VGX-3100 and the CELLECTRA™ device represent an integrated Investigational Product (IP) designed as a non-surgical treatment of HPV-16/18-related anal or anal/peri-anal HSIL (AIN2, AIN3, PAIN2, and PAIN3) via an immune response directed against HPV-16/18.

The initial formulation of VGX-3100 was Water for Injection (WFI) with 1% w/w poly-L-glutamate (WFI/LGS) that required frozen storage. This frozen formulation has been administered to more than 250 subjects in Phase 1 and 2 clinical trials. A buffered formulation of VGX-3100 was developed using a saline sodium citrate (SSC) solution, which is stored non-frozen (5°C). This non-frozen formulation of VGX-3100 was administered to 117 subjects in a Phase 1 clinical trial, HPV-101 in which subjects were randomized 1:1 to receive the non-frozen or frozen formulation of VGX-3100. In study HPV-101, healthy adults received three 6 mg IM doses of VGX-3100 in the frozen or non-frozen formulations followed by EP with the CELLECTRA™ 5Pdevice. The non-frozen formulation was found to be non-inferior to the frozen formulation based upon a 2-fold rise in overall Spot Forming Units (SPU) to the antigens encoded by the plasmids per 10⁶ Peripheral Blood Mononuclear Cells (PBMC) as measured from baseline to Week 14 using the interferon-γ enzyme-linked immunospot (ELIspot) assay.

Proof of concept was demonstrated in the prospective, randomized, double blind, placebo-controlled Phase 2b study of VGX-3100 (frozen formulation) followed by EP in the treatment of high grade cervical dysplasia, cervical HSIL associated with HPV-16/18 [1]. The Phase 2b study, HPV-003, enrolled 169 subjects with high grade cervical dysplasia from seven countries and one US Territory (Australia, Canada, Estonia, Republic of Georgia, India, South Africa, US and Puerto Rico). Subjects were randomized in a 3:1 ratio to treatment with VGX-3100 or placebo, respectively. All

subjects were to receive treatment on Day 0, Week 4 and Week 12. All subjects were to repeat cervical biopsy or Loop Electrical Excision Procedure (LEEP) of the cervix at Week 36 to assess efficacy defined as regression of high grade Cervical Intraepithelial Neoplasia (CIN) by histopathology. The primary endpoint was histopathologic regression of cervical lesions (CIN2 or CIN3) to Grade 1 Cervical Intraepithelial Neoplasia (CIN1) or less at the Week 36 visit. A secondary endpoint was clearance of HPV-16/18 in combination with histopathologic regression of cervical lesions to CIN1 or less. The proportions of subjects who met the primary and secondary endpoints were significantly higher in the VGX-3100 group vs. placebo in both per protocol (PP) and modified Intent to Treat (mITT) analyses. Robust T-cell activity was detected in VGX-3100 recipients compared to placebo recipients. VGX-3100 was generally safe and well tolerated when administered intramuscularly with electroporation.

